## 8 CONVENTIONS

### 8.1 General

The following conventions may be used for imputing partial dates for analyses requiring dates:

- For missing and partial adverse event onset dates, imputation will be performed using the Adverse Event Domain Requirements Specification
- For missing and partial adverse event resolution dates, imputation will be performed as follows (these conventions may change):
  - If only the day of the month is missing, the last day of the month will be used to replace the missing day. If the imputed date is after the death date or the last known alive date, then the latest known alive date or death date is considered as the resolution date.
  - If the day and month are missing or a date is completely missing, it will be considered as missing.
- Missing and partial non-study medication domain dates will be imputed using the derivation algorithm described in 4.1.3 of BMS Non-Study Medication Domain Requirements Specification.
- Missing and partial radiotherapy and surgery dates will be imputed using algorithm described in [APPENDIX 1](#).
- For death dates, the following conventions will be used for imputing partial dates:
  - If only the day of the month is missing, the 1st of the month will be used to replace the missing day. The imputed date will be compared to the last known alive date and the maximum will be considered as the death date.
  - If the month or the year is missing, the death date will be imputed as the last known alive date.
  - If the date is completely missing but the reason for death is present, the death date will be imputed as the last known date alive.
- For other partial/missing dates, the following conventions were used:
  - If only the day of the month is missing, the 15th of the month will be used to replace the missing day.
  - If both the day and the month are missing, “July 1” will be used to replace the missing information.
  - If a date is completely missing, it will be considered as missing.

The following conversion factors will be used to convert days to months or years:

1 month = 30.4375 days and 1 year = 365.25 days.

Duration (e.g. time-to onset, time-to resolution) will be calculated as follows:

$$\text{Duration} = (\text{Last date} - \text{first date} + 1)$$

Last known alive date will be defined based on all appropriate dates collected on the CRF.

All statistical analyses will be carried out using SAS (Statistical Analysis System software, SAS Institute, North Carolina, USA) unless otherwise noted.

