8.3 Lost to Follow-Up

All reasonable efforts must be made to locate participants to determine and report their ongoing status. This includes follow-up with persons authorized by the participant.

- Lost to follow-up is defined by the inability to reach the participant after a minimum of **three** documented phone calls, faxes, or emails as well as lack of response by participant to one registered mail letter. All attempts should be documented in the participant's medical records.
- If it is determined that the participant has died, the site will use permissible local methods to obtain date and cause of death.
- If investigator's use of third-party representative to assist in the follow-up portion of the study has been included in the participant's informed consent, then the investigator may use a Sponsor retained third-party representative to assist site staff with obtaining participant's contact information or other public vital status data necessary to complete the follow-up portion of the study.
- The site staff and representative will consult publicly available sources, such as public health registries and databases, in order to obtain updated contact information.
- If after all attempts, the participant remains lost to follow-up, then the last known alive date as determined by the investigator should be reported and documented in the participant's medical records.

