### **4.1.2 Duration of Response**

Duration of Response (DOR) is defined as the time between the date of first confirmed documented response (CR or PR) to the date of the first documented tumor progression as determined by the investigator (per RECIST v1.1 criteria), or death due to any cause, whichever occurs first. Subjects who start subsequent therapy without a prior reported progression will be censored at the last evaluable tumor assessments prior to initiation of the subsequent anticancer therapy. Subjects who die without a reported prior progression will be considered to have progressed on the date of their death. Subjects who neither progress nor die, DOR will be censored on the date of their last evaluable tumor assessment. DOR will be evaluated for responders (confirmed CR or PR) only.

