### **7.6.1      Deaths**

Deaths will be summarized:

- All deaths, reasons for death.
- Deaths within 100 days of last dose received, reasons for death.

A by-subject listing of deaths will be provided for the all enrolled subjects population.

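### A death with a recorded year but no month is dated to the last known alive date, which contradicts the case report form when that date falls in an earlier year

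*SAP*

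**What the plan says.** SAP 8.1 gives three rules for incomplete death dates.

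- Day missing only: take the first of the recorded month, and then "The imputed date will be compared to the last known alive date and the maximum will be considered as the death date".
- Month or year missing: "If the month or the year is missing, the death date will be imputed as the last known alive date".
- Date wholly missing but a reason for death present: use the last known alive date (LKAD).

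On LKAD itself the SAP says only this: "Last known alive date will be defined based on all appropriate dates collected on the CRF". The list opens permissively ("The following conventions may be used for imputing partial dates for analyses requiring dates"), but the death-date item is worded as a firm rule and no alternative is offered.

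Two planned outputs depend on the death date. SAP 7.6.1 summarises all deaths and, separately, "Deaths within 100 days of last dose received, reasons for death". SAP 4.1.2 makes death a DOR event: "Subjects who die without a reported prior progression will be considered to have progressed on the date of their death".

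**The concern.** The second rule joins two different situations. If the year is unknown, LKAD is a sensible fallback. If the year is known and only the month and day are missing, the rule throws away recorded information. When the recorded year is later than the LKAD year, the analysis date is one that the CRF shows to be wrong, and it is always too early.

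The SAP does not do this elsewhere. The day-missing rule keeps the recorded month and year. Appendix 1 places a year-only procedure date at the later of 1 January of that year and first dose. The convention for other dates in SAP 8.1 places a year-only date at 1 July of that year. Among the SAP's year-only rules that impute a date, only the death rule discards the year.

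Year-only deaths are conceivable here. Required follow-up ends about 100 days after last dose, or 30 days after BMS-986205 alone (Protocol 5.1). Investigators need not seek later events actively (Protocol 9.2.1). For participants who cannot be reached, Protocol 8.3 says: "If it is determined that the participant has died, the site will use permissible local methods to obtain date and cause of death". At stake are the 100-day death table and, for a few responders, DOR.

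**Working it through.** The documents state no figure that depends on this rule, so there is none to reproduce. The check applies the rule as written and compares it with the earliest date that the record allows.

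**Rules compared, for year Y recorded and month missing**

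- SAP 8.1: death date = LKAD.
- Floor: death date = max(01-Jan-Y, LKAD). This is the SAP's day-missing logic carried up one level.

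If LKAD already falls in year Y, the two agree. If LKAD falls in an earlier year, the SAP date always contradicts the recorded year.

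**When the 100-day table is certainly wrong.** Both conditions must hold:

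1. LKAD − last dose ≤ 100 days.
2. 01-Jan-Y − last dose > 100 days.

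For a death recorded as 2021, condition 2 means a last dose on or before 22-Sep-2020 (01-Jan-2021 minus 101 days).

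**Illustrations.** All dates are assumptions; none comes from the documents. First response is 01-May-2020, with no progression and no subsequent therapy. Days are simple differences from last dose. DOR in months = (event date − first response + 1) / 30.4375, using the duration convention and conversion factor in SAP 8.1.

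| Last dose | LKAD | Recorded death | Day, SAP rule | Day, floor | DOR, SAP rule | DOR, floor |
|---|---|---|---|---|---|---|
| 01-Aug-2020 | 10-Oct-2020 | 2021 | 70 | 153 | 5.4 | 8.1 |
| 01-Sep-2020 | 20-Nov-2020 | 2021 | 80 | 122 | 6.7 | 8.1 |
| 01-Sep-2020 | 01-Dec-2020 | 2022 | 91 | 487 | 7.1 | 20.1 |
| 01-Dec-2020 | 20-Dec-2020 | 2021 | 19 | 31 | 7.7 | 8.1 |

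Second row in full:

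- SAP rule: 20-Nov-2020 − 01-Sep-2020 = 80 days, counted as within 100 days. DOR = (203 + 1) / 30.4375 = 6.7 months.
- Floor: 01-Jan-2021 − 01-Sep-2020 = 122 days, not counted. DOR = (245 + 1) / 30.4375 = 8.1 months.
- Latest date the record allows: 31-Dec-2021, Day 486. DOR = (609 + 1) / 30.4375 = 20.0 months.

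In the first three rows the SAP rule counts a death that cannot have occurred within 100 days. In the fourth, both rules place it inside the window.

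The SAP does not say whether its plus-one duration convention applies to the 100-day window. Here it does not matter: Day 80 becomes 81 and Day 122 becomes 123.

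**Weight of one case.** 1/12 = 8.3 percentage points if exactly 12 participants are treated. Twelve is the PK-evaluable target, and participants who discontinue before or at Cycle 1 Day 1 are replaced (Protocol 5.2). Safety tables use all treated subjects (SAP 6.3, 7.6). With 13 treated, for example, it is 1/13 = 7.7 points.

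**The case against.** The strongest reply is that this is a rare edge case with limited reach. Most of that stands.

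- Deaths are among the primary safety endpoints, so a reader might infer that the primary death result is at risk. It is not. Imputing a date cannot change the count of all deaths, and the by-subject listing in SAP 7.6.1 makes each death visible.
- A reader might also infer that any death after scheduled follow-up is pulled into the 100-day table. The final visit is at Day 100 ± 10 days. If LKAD is Day 101 to 110, the imputed date stays outside the window (on simple day differences). The exposed group is mainly participants whose LKAD precedes or falls at that visit.
- The DOR effect is narrow. Death matters only in a confirmed responder without prior progression, and subsequent therapy removes it: "Subjects who start subsequent therapy without a prior reported progression will be censored at the last evaluable tumor assessments".
- The documents give no basis for how often a death would be recorded by year only.

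The reply also says that LKAD is the conservative choice for DOR, because the floor credits time with no tumor assessment behind it. In the second row that is 122 − 80 = 42 days; in the third, 487 − 91 = 396 days. This is a real cost. However, SAP 4.1.2 already counts a fully dated death as an event on its date, with no limit on the gap since the last scan. The floor treats a year-only death in the same way. Conservatism for DOR also does not justify a false entry in the safety table.

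**Conclusion.** The point holds as a minor error in a stated rule. Whenever the recorded year of death is later than the LKAD year, SAP 8.1 produces a date that contradicts the CRF, and no other section corrects it. That follows from the wording and needs no assumed data.

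The effect on results is conditional. The 100-day table is certainly wrong only under the two conditions in the working. DOR is shortened only in a confirmed responder with neither progression nor subsequent therapy beforehand. One misplaced death is at most about 8 percentage points, assuming 12 treated participants. The day counts and DOR values are illustrations on assumed dates. Few participants, possibly none, will be affected, and the study has no survival endpoint. The documents do not support reading this as a threat to the primary conclusions.

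**What to change.** Replace the sentence in SAP 8.1 with: *If the month is missing and the year is known, impute 01 January of that year, compare with the last known alive date and use the later; if the year is missing, use the last known alive date.*

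Also flag imputed death dates in the deaths and DOR listings, so that a reader can see which entries rest on a convention.

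The cost is one SAP sentence, one line of code and a listing flag. Nothing changes when LKAD already lies in the recorded year. There are two small downsides. The floor is still the earliest possible date, so some shortening remains. It can also credit DOR time that no tumor assessment supports. The flag makes both visible.

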## 8.2 Pharmacokinetic Summaries

### In-text Tables

For in-text pharmacokinetic tables, coefficient of variation (%CV) will be reported as integers. For other statistics except for standard deviations, values of 100 or higher will be presented as integers, values of 10 - < 100 will be displayed to one decimal place, and values of 1 - < 10 will be displayed to two decimal places. Values less than 1 will be displayed to three decimal places. Ratios will also be displayed to three decimal places. Standard deviations will be reported to a precision of 1 decimal place more than the mean.

### Handling of Non-Quantifiable Concentrations

For the summaries of PK concentration-time data, concentrations that are less than the lower limit of quantification (LLOQ) should be displayed as “< LLOQ” in the listings and be treated as missing in summary tables and plots. For the purpose of calculating PK parameters, other than Ctrough, pre-dose concentrations that are less than LLOQ and concentrations prior to the first quantifiable concentration that are less than LLOQ will be set to zero, and all other concentrations less than LLOQ will be set to missing. Summary statistics for Ctrough concentrations will be calculated by imputing values less than LLOQ as  $\frac{1}{2} * \text{LLOQ}$ .

All available PK concentration-time data and derived pharmacokinetic parameter values will be included in the PK data set and listed accordingly.

### Treatment of Outliers

Individual PK concentrations, if deemed to be anomalous, may be excluded from the analysis following a review of available documentation (e.g., bioanalytical report, clinical data). Any such exclusion will be clearly listed in the study report along with justification for exclusion.

Entire PK concentration-time profiles for a subject may be excluded following review of available documentation (e.g., bioanalytical report, clinical data). However, results of analysis with and without the excluded profiles may be presented in the study report. Any such exclusion will be clearly listed in the study report along with justification for exclusion.

### PK Exclusions

PK Analysis, Reporting, and Exclusion criteria should follow the BMS PK Harmonization document Version 4.0.

## **9 CONTENT OF REPORTS**

The complete list of analyses contributing to the clinical study report and other possible analyses will be given in the Data Presentation Plan.

## **10 DOCUMENT HISTORY**

**Table 10-1: Document History**

| Version Number | Author(s) | Description |
|-----------------------|------------------|--------------------|
| 1.0                   |                  | Original Issue     |

## **APPENDIX 1      MISSING AND PARTIAL RADIOTHERAPY AND SURGERY DATES IMPUTATION ALGORITHMS**

### **Procedures – Imputation Rules.**

If reported procedure start date is a full valid date then set start date equal to the date part of procedure start date.

In case of partial date use imputation rules described below:

- If only day is missing then
  - If month and year of procedure match month and year of first dose date then impute as date of first dose;
  - If month and year of procedure don't match month and year of first dose date then impute as first day of that month and year.
- If both day and month are missing, then impute as maximum between 01JAN of the year and date of the first dose;
- If date is completely missing or invalid then leave missing.

Note: Imputation is not applicable to data where start date is not collected (for example "PRIOR RADIOTHERAPY" CRF). Set start date to missing in this case.

If reported end date is a full valid date then set end date equal to the date part of the reported end date.

In case of partial date use imputation rules described below:

- If reported end date is partial then set end date equal to the last possible reported end date based on the partial entered reported end date.
- If reported end date is missing, continuing, unknown or invalid then set end date equal to the most recent database extraction date.

If end date was imputed then compare end date to the death date or last known alive date if subject is not dead. If posterior then end date should be imputed to death date (or last known alive date if subject not dead).

Note: Imputation of partial dates only applies to data entered on "RADIOTHERAPY" CRF page. For other CRF pages in case of partial dates set end date to missing.

### **Surgeries – Imputation Rules.**

If reported surgery date is a full valid date then set start date equal to the date part of surgery date.

In case of partial date, use one of the two imputation rules described below:

A. For data collected on "PRIOR SURGERY RELATED TO CANCER" CRF page:

- If only day is missing then impute as the first day of the month;

[figure not shown]
- If both day and month are missing then then impute as 01JAN of the year;
- If date is completely missing or invalid then leave missing.

[figure not shown]
B. For data collected on other CRF pages (deemed to be on-treatment/subsequent surgeries):

- If only day is missing then
  - If month and year of surgery match month and year of first dose date then impute the missing date as the date of first dose;
  - If month and year of surgery don't match month and year of first dose date then impute as first day of that month and year;
- If both day and month are missing then impute as maximum between 01JAN of the year and date of the first dose;
- If date is completely missing or invalid then leave missing.

**APPENDIX 2**

**IMMUNOGENICITY ANALYSIS**

## Immunogenicity Endpoints

A fundamental metric that informs clinical immunogenicity interpretation is the incidence of ADA in a study or across comparable studies. ADA incidence is defined as the proportion of the study population found to have seroconverted or boosted their pre-existing ADA during the study period.

## Terms and Definitions

Validated ADA test methods enable characterization of samples into ADA-positive vs. ADA-negative. To classify the ADA status of a subject using data from an in vitro test method, each sample from the subject is categorized based on the following definitions:

### Sample ADA Status:

- Baseline ADA-positive sample: ADA is detected in the last sample before initiation of treatment
- Baseline ADA-negative sample: ADA is not detected in the last sample before initiation of treatment
- ADA-positive sample: After initiation of treatment, (1) an ADA detected (positive seroconversion) sample in a subject for whom ADA is not detected at baseline, or (2) an ADA detected sample with ADA titer to be at least 4-fold or greater ( $\geq$ ) than baseline positive titer
- ADA-negative sample: After initiation of treatment, ADA not positive sample relative to baseline

Next, using the sample ADA status, subject ADA status is defined as follows:

### Subject ADA Status:

- Baseline ADA-positive subject: A subject with baseline ADA-positive sample
- **ADA-positive subject:** A subject with at least one ADA positive-sample relative to baseline at any time after initiation of treatment

- 1) *Persistent Positive (PP):* ADA-positive sample at 2 or more consecutive time points, where the first and last ADA-positive samples are at least 16 weeks apart
- 2) *Not PP-Last Sample Positive:* Not persistent positive with ADA-positive sample at the last sampling time point

- 3) *Other Positive*: Not persistent positive but some ADA-positive samples with the last sample being negative
- 4) *Neutralizing Positive*: At least one ADA-positive sample with neutralizing antibodies detected
  - **ADA-negative subject**: A subject with no ADA-positive sample after the initiation of treatment.

(Note: 16 weeks was chosen based on a long half-life of IgG4.)

### **Population for Analyses**

Analysis of immunogenicity data will be based on ADA evaluable subjects defined as all treated subjects with baseline and at least 1 post-baseline immunogenicity assessment. Analysis dataset and data listing will include all available ADA samples. However, subject-level ADA status will be defined based on only adequate samples (e.g., excluding 1-hour post-infusion samples when clearly indicated).
